#### Benefits.

Real-time CGM provides benefits beyond the information one gets from a blood glucose meter. It provides glucose readings every five minutes for up to seven days to help detect trends and patterns in glucose levels. This trend information can help you see where the glucose is now as well as where the glucose may be heading and how fast the patient may be getting there. Understanding the glucose trends may help take action to help avoid high or low glucose values. Alerts and the low alarm tell when your glucose is outside of the target glucose range and may help avoid low and high blood sugar. Rise and fall glucose alerts can also provide benefit by alerting when your glucose is rapidly going down or up. This way the patient can be alerted to this information before the glucose is too high or too low and take action to avoid it. Real-time CGM can help increase time in the target glucose range without increasing time in the low or high glucose range. Real-time CGM can help improve diabetes control (lower A1c values, reducing glycemic variability and time spent in low and high blood glucose ranges) which can help reduce diabetes related complications. In some cases, patients perceived an increase in their quality of life and peace of mind when using real-time CGM as well as reporting a high satisfaction with CGM.

#### Inserting the Device.

[figure not shown]
It is necessary to choose an area that is at least 7.62 cm from where the insulin can be injected or from where the pump infusion site is located.

1. Clean the area first with an alcohol wipe. Make sure the area is clean and completely dry before the sensor is inserted.
2. Using the white tabs on the adhesive backing, remove the adhesive backing from the sensor pod one half at a time. Hold the sensor by the applicator barrel and try not to touch the sticky adhesive patch.
3. Place the sensor flat on the selected area, to the left or right of the belly button. Make sure the sensor is placed in the same direction shown in the picture below. One not place the sensor pointing in the up or down direction.

[figure not shown]
CONFIDENTIAL

This material is the property of the NYU School of Medicine and Langone Medical Center. Do not disclose or use except as authorized in writing by the study sponsor

Use of continuous glucose monitoring system with intensive feedback in adolescents with poorly controlled type 1 diabetes  
Version Date: 04/26/2018

[figure not shown]
[figure not shown]

**Remove the adhesive backing**

**Adhere the sensor on the skin**

4. Press the finger firmly around the adhesive patch to make sure it is smooth.
5. Hold on to the applicator. Then pull the safety lock straight out away from the applicator, in the direction the arrows show in the following picture.

**Remove the safety lock**

Once the sensor is inserted, we need to snap the transmitter into the sensor pod. Follow the steps below to attach the transmitter.

1. Clean and dry the bottom of the transmitter with a damp cloth or an alcohol wipe before every use.
2. Place the transmitter in the sensor pod with the flat side facing down.

CONFIDENTIAL

This material is the property of the NYU School of Medicine and Langone Medical Center. Do not disclose or use except as authorized in writing by the study sponsor

Use of continuous glucose monitoring system with intensive feedback in adolescents with poorly controlled type 1 diabetes  
Version Date: 04/26/2018

## Install transmitter in sensor pod

3. With one hand, pinch up on your skin at the front edge of the white adhesive.
  - a. Place one finger on the transmitter to keep it in place while securing the transmitter into the sensor pod.
  - b. Pull the transmitter latch over the transmitter to snap the transmitter into place. The transmitter should lie flat in the sensor pod. We should hear 2 “clicks.” If we do not hear 2 “clicks,” the transmitter might not be fully snapped in. We can release your pinch on the adhesive edge at this time.
  - c. Make sure the transmitter is secure by sliding your first and second fingers under the sensor pod wings and press down on the transmitter with your thumb.

4. Hold the transmitter in place with one hand. Using your other hand, remove the transmitter latch by holding the end of the latch and quickly twisting off the latch away from your body.

CONFIDENTIAL

This material is the property of the NYU School of Medicine and Langone Medical Center. Do not disclose or use except as authorized in writing by the study sponsor

Use of continuous glucose monitoring system with intensive feedback in adolescents with poorly controlled type 1 diabetes  
Version Date: 04/26/2018

## Remove transmitter latch

The use of the CGMS (Dex-COM ®) device will be explained and the device placed on the subject's abdomen by a trained study personnel. The participant will be instructed to continue to perform capillary glucose testing as usual at home, and to calibrate the Dex-COM ® at least twice daily. The participant will be encouraged to review the CGMS readings as often as possible, particularly before meals, bedtime, and 1-2 hours after eating. If the glucose result on the CGMS is  $\geq 300$  mg/dl, or  $\leq 80$  mg/dl, he/she will be instructed to verify the results by using the glucose meter, follow the usual care instructions and then call the Pediatric Diabetes team for advice. An alarm upper limit will be set on the CGMS device at 300 mg/dl, and a lower limit at 80 mg/dl. He/she and the investigator will agree on a time of day for daily phone contact. The phone advice will be based on standard medical management of type 1 diabetes mellitus, focusing on details of insulin dosing, carbohydrate counting, and exercise. A tally will be kept of the number of daily phone calls completed with the medical staff and the participant. The parent will be able to speak to the medical staff during phone calls, but the primary contact will be with the adolescent participant.

2: Study visit # 2 will be in 1 week from the initial visit for both the study and control groups. The patients in the study group will return the CGMS device at the time of the 1 week appointment. The glucose meters of all participants will be downloaded, and the data will be extracted as above. The Empowerment Scale short form and the measure of Stages of Change will be administered to both groups. A brief questionnaire about the participant's response to use of CGMS will be given to the study group (CGM Satisfaction scale – Appendix F). Study and control groups will both be given a \$50

CONFIDENTIAL

This material is the property of the NYU School of Medicine and Langone Medical Center. Do not disclose or use except as authorized in writing by the study sponsor

Use of continuous glucose monitoring system with intensive feedback in adolescents with poorly controlled type 1 diabetes  
Version Date: 04/26/2018

reimbursement for time and travel.

3. Study visit #3 will be scheduled at 1 month for both the study and control groups. The patient's glucose meter will be downloaded and the data will be extracted as above. The Empowerment Scale short-form, Quality of Life, Family Management Measure and the Stages of Change questionnaires will be administered. There will be an open-ended interview with the participant. The patient will be given \$20 on completion at this visit.

4: Study visit #4 will be scheduled at 3 months for both the study and control groups. The patient's HbA1c will be measured in the lab at the location of the patient's visit, his/her glucose meter will be downloaded and the data will be extracted as above. The Empowerment Scale short-form, PHQ-2, Quality of Life and the Stages of Change questionnaires will be administered. The patient will be given \$20 on completion at this visit.

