#### CONFIDENTIAL

This material is the property of the NYU School of Medicine and Langone Medical Center. Do not disclose or use except as authorized in writing by the study sponsor

Use of continuous glucose monitoring system with intensive feedback in adolescents with poorly controlled type 1 diabetes  
Version Date: 04/26/2018

appointments and staff will determine if they are interested in participation in the study using a recruitment script uploaded under recruitment materials section.

The study is minimal risk (MR). The device is approved by the FDA and is being used according to its cleared/approved labeling. The probability and magnitude of harm or discomfort anticipated in this research is similar to those ordinarily encountered in daily life or during the performance of routine physical or psychological examinations or tests.

The use of the CGMS will be described.

The study will consist of 4 phases.

1: For all participants at entry into the study the participant's HbA1c will be measured in the lab at the location of the patient's visit and his/her glucose meter will be downloaded as part of routine care. The average capillary glucose level, (with range and standard deviation) and the average number of tests per day over the prior 14 days will be recorded. The current individual care plans for self-management of type 1 diabetes will be reviewed by the study personnel with the participant.

Questionnaires will be administered to all the participants except Appendix F:

- 1) Appendix A - Stages of Change measure (original). We created a 5 item questionnaire to assess the patient's current stage.
- 2) Appendix B - Psychosocial self-efficacy (University of Michigan Diabetes Research and Training Diabetes Empowerment Scale short-form) - DES. 8 items. Also available for use.(3-6)
- 3) Appendix C - Knowledge and risk perception (University of Michigan Diabetes Research Training Center Diabetes Knowledge Scale). 23 items - DKT. We are substituting rapid acting insulin for NPH insulin in item 17 since NPH is not used in our study population. Available for use without permission as long as the source is quoted.(7, 8)
- 4) Appendix D - Quality of life (Peds QL 3.2, Diabetes module,) – Peds QL. 33 items on a Likert scale.(9)

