- 5) Appendix E - Depression (PHQ-2.). 2 items. If the patient receives a score of 3 or above, a referral to psychiatric services will be made. No permission required to reproduce, translate, display or distribute.(10, 11)
- 6) Appendix F – CGM Satisfaction Scale. To be administered at second visit. See below number 2 on protocol. Will only be administered to study group.
- 7) Appendix G - Demographic variables will be collected.
- 8) Appendix H - Telephone administered questionnaire.
9. Appendix I – data to be tabulated in research database in RedCap

---

[figure not shown]
CONFIDENTIAL

This material is the property of the NYU School of Medicine and Langone Medical Center. Do not disclose or use except as authorized in writing by the study sponsor

Use of continuous glucose monitoring system with intensive feedback in adolescents with poorly controlled type 1 diabetes  
 Version Date: 04/26/2018

Standard scoring will be used for the DKT, DES, PHQ-2 and Peds QL.  
 Standard scoring instructions will be followed for published tests.  
 The CGMS will be used only in the study group. The CGMS that will be used will be Dex-COM® which consists of the sensor, transmitter and the receiver. The Dex-COM CGM device is FDA approved for use in patients 2 years and older.

**Sensor** - The sensor is packaged in a sterile sealed pouch, containing an applicator, sensor pod and sensor wire. The applicator barrel helps to insert the sensor wire inside the sensor pod under the skin. After inserting the sensor wire, the applicator barrel is removed. The sensor wire stays in the sensor pod with the pod attached to the skin by adhesive. The sensor wire is made of silver and platinum with polymer membranes. Once inserted, the thin and flexible wire measures the glucose levels in the fluid between the cells (interstitial fluid) for up to seven days. Dexcom sensor is inserted in the belly/abdomen (ages 2 years and older) or the upper buttocks (ages 2 to 17 years). The sensor is water resistant

**Transmitter** - Snapping into the sensor pod, the gray plastic transmitter wirelessly sends your glucose information to your display devices—receiver. The transmitter is re-usable and water-resistant.

CONFIDENTIAL

This material is the property of the NYU School of Medicine and Langone Medical Center. Do not disclose or use except as authorized in writing by the study sponsor

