#### ANALYSIS:

Measures of the level of glycemic control will be assessed primarily by HbA1c and secondarily by the average glucose tests results on the patient's glucose meter. Comparison of the glucose results (average, range, standard deviation, number of daily tests) between the study entry, 1 week, 1 month and 3 month follow up visits will be done. Comparison of HbA1c at entry and at 3-month follow-up will be performed. Questionnaire scores will be compared between study entry, 1 week follow up, 1 month follow up and 3-month follow-up visits for DES and Stages of Change scales. We will determine if there is a correlation between the scores on the questionnaires and measures of glucose control. We will classify study and control participants into adherent and non-adherent groups.

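### Read with the only look-back stated, week-1 tests per day shares seven days with baseline; CGM-prompted meter checks add a caveat in one arm

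*Combined protocol and SAP*

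**What the plan says.** METHODS, phase 1 (entry) lists four meter summaries: average capillary glucose, its range, its SD, and tests per day. The only time window comes at the end of that list: "the average number of tests per day over the prior 14 days will be recorded". It attaches to the test count. Whether it also covers the average, range and SD is not said.

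Phase 2 puts visit 2 one week after entry in both groups and says "The glucose meters of all participants will be downloaded, and the data will be extracted as above". Phases 3 and 4 (1 and 3 months) use the same back-reference: "glucose meter will be downloaded and the data will be extracted as above".

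ANALYSIS plans a "Comparison of the glucose results (average, range, standard deviation, number of daily tests) between the study entry, 1 week" and the two later visits. It ranks the measures: glycaemic control is "assessed primarily by HbA1c and secondarily by the average glucose tests results". Statistical methods then names a 7-day meter average, with change categories cut at ±15 (no unit printed). It does not say which visits this applies to, and it gives no window for range, SD or test count.

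On the device, "The CGMS will be used only in the study group". The wearer is to "continue to perform capillary glucose testing as usual at home", to calibrate at least twice daily and, when the CGM shows ≥300 or ≤80 mg/dl, "he/she will be instructed to verify the results by using the glucose meter". There is no counterpart for controls, and no rule on how such readings enter the meter summaries.

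**The concern.** A change from baseline should set time after entry against time before it. A 14-day look-back taken on day 7 reaches back a week before entry, into days that the baseline figure already used. The reported change then mixes the effect of the first week with data that cannot show one.

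The stated aim is whether short-term CGM with feedback affects motivation or behaviour. Tests per day is the behavioural measure among the meter summaries, and visit 2 is the visit at the end of the device week. A change reported on the wrong scale there could be misread.

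The second issue does not depend on the window. The CGM itself prompts meter tests in one arm, and the verification prompts come at extreme values. Any such tests beyond routine ones enter that arm's test count, average, range and SD as though they were ordinary self-monitoring.

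**Working it through.** The plan gives no figure to reproduce here. The inputs from the documents are the 14-day look-back (METHODS, phase 1), the 7-day gap to visit 2 (phase 2), and the 7-day average and ±15 limits (Statistical methods).

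**1. Overlap.** Shared days = max(0, window − gap).
- Visit 2, 14-day window: 14 − 7 = 7 days, or 7/14 = 50% of the window.
- Visit 2, 7-day window: 0.
- Visits at about 30 and 90 days, either window: 0.

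**2. Tests per day.** Let A, B and C be mean tests per day in days −14 to −8, −7 to −1 and 1 to 7. Baseline = (A + B)/2 and week 1 = (B + C)/2, so the reported change = (C − A)/2. If A = B, this is (C − B)/2, half the true change: rises of 1, 2 and 4 per day are reported as 0.5, 1 and 2. If A ≠ B, it is not half (illustrative values):

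| A, B, C | Overlapping change | C minus 14-day baseline | C minus 7-day baseline |
|---|---|---|---|
| 4, 4, 6 | 5 − 4 = 1 | 6 − 4 = 2 | 6 − 4 = 2 |
| 3, 5, 6 | 5.5 − 4 = 1.5 | 6 − 4 = 2 | 6 − 5 = 1 |
| 5, 3, 6 | 4.5 − 4 = 0.5 | 6 − 4 = 2 | 6 − 3 = 3 |

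In the second row the overlapping figure is larger than the change from a 7-day baseline.

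**3. Average glucose, only if the 14-day phrase governs it.** Pooled over readings, with r tests per day before entry and r + k in week 1, and steady glucose and testing before entry, the share of the true change that is reported is (r + k)/(2r + k).
- k = 0: 0.50. A true change of 30 is needed to show 15.
- r = 4, k = 2: 6/10 = 0.60. A true change of 15/0.60 = 25 is needed.
- r = 8, k = 1: 9/17 = 0.53.

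Under the 7-day average in Statistical methods, this dilution is zero.

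**4. Effect on a paired comparison.** Assume independent days with SD s and a true change d.
- Overlapping 14-day windows: signal d/2, noise s√(2/7)/2 = 0.267s, ratio 1.87 d/s.
- Separate 7-day windows: signal d, noise s√(2/7) = 0.535s, ratio 1.87 d/s.
- Days 1 to 7 against the prior 14 days: signal d, noise s√(1/7 + 1/14) = 0.463s, ratio 2.16 d/s.

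The overlap shrinks signal and noise together. With steady pre-entry testing it distorts the reported size, not detectability relative to separate 7-day windows.

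**5. Device-prompted checks.** The documents give no glucose distribution and no number of extra checks, so these inputs are assumptions: routine readings with mean 220 and SD 80 mg/dl, high checks averaging 330 (SD 20), low checks averaging 70 (SD 8), r routine and k extra tests per day, no change in glycaemia. With t the mean of the extra checks, the shift in the average is k(t − 220)/(r + k).
- r = 4, k = 1, all high: 110/5 = +22. Half high (t = 200): −20/5 = −4. All low: −150/5 = −30.
- r = 2, k = 2, all high: 2 × 110/4 = +55. Half high: 2 × (−20)/4 = −10.
- The shift is zero when the low share is (330 − 220)/(330 − 70) = 0.42.
- SD at r = 2, k = 2: all high, √[0.5(6400 + 55²) + 0.5(400 + 55²)] = 80. Half high (overall mean 210), √[0.5(6400 + 10²) + 0.25(400 + 120²) + 0.25(64 + 140²)] = 109.

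On top of unchanged routine testing, the count rises by k and the range can only widen or stay the same. If routine tests double as checks, k = 0 and nothing moves.

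**The case against.** The back-reference at visit 2 may mean the same data items rather than the same look-back. For the average, Statistical methods already names 7 days, which fits the one-week interval. That stands for the average. It leaves range and SD without a window, and the test count with no window other than 14 days.

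A reader might infer that the week-1 change is always understated by half. The formula does not support this: it holds only with equal testing in the two pre-entry weeks, and step 2 shows cases on either side.

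A reader might also infer that the CGM arm's meter glucose is biased by a known amount. The documents do not support that either. They do not say that calibration uses a meter reading or adds to routine tests, routine tests may serve as checks, and every mg/dl figure in step 5 rests on assumed inputs. What survives is that the prompts exist in one arm only.

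Finally, the consequences are limited. HbA1c is the primary glycaemic measure, no between-arm test of meter data at week 1 is stated, and a paired comparison is not weakened relative to separate 7-day windows. This is right and sets the severity.

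**Conclusion.** The point holds, at minor severity. With the only look-back stated for it, the week-1 test count includes seven days that are also in the baseline, and the plan compares the two. The reported change is half the true change if pre-entry testing was steady, and may be a larger or smaller fraction otherwise. The average, range and SD share the problem only on the wider reading of the 14-day phrase.

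The verification and calibration instructions are a real difference between the arms at week 1, under either window. They support a caveat on interpretation, not an estimate of bias.

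It would be wrong to read this as a threat to the trial's main glycaemic result. HbA1c does not come from the meter, and the 1- and 3-month windows do not reach back to entry.

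**What to change.** Reconcile METHODS (phases 1 and 2) with Statistical methods. State that at visit 2 the meter average, range, SD and tests per day come from days 1 to 7 after entry only, and are compared with a pre-entry window that does not overlap it: the 14 days of phase 1 or the 7 days of Statistical methods. For the range, equal 7-day windows are preferable, because a range tends to widen as readings accumulate. The 1- and 3-month windows need no change on this account, and week 1 can remain a planned comparison.

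Add that a week-1 difference in meter measures in the CGM arm may partly reflect device-prompted checks, so conclusions on self-monitoring and meter glucose should be confirmed at 1 and 3 months.

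The cost is a change of wording; the same downloads serve. The downside is that a 7-day figure is noisier than a 14-day one, by √(14/7) = 1.41 if days are independent.

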#### CONSENT:

The study personnel will describe the procedures: filling out the questionnaires, wearing the CGMS device for 1 week, participating in daily phone calls with study personnel for the 1 week when the device is used, and the requirements of returning the CGMS device, and of bringing the glucose meter to all appointments. The participant and his/her parent must sign the consent for these items. The study personnel will change the sensor in 1 week to put a new sensor for the second week.

The use of the CGMS device involves the insertion of a subcutaneous sensor that will transmit data to the CGMS receiver which is carried by the subject. Minor skin irritation or bruising may occur, and there is a low risk of skin infection. Restrictions in terms of submersion in water will be described and consented. The Dex-Com ® CGMS device is FDA approved for use in children and adolescents with type 1 diabetes.

#### ANALYSIS:

Measures of the level of glycemic control will be assessed primarily by HbA1c and secondarily by the average glucose tests results on the patient's glucose meter. Comparison of the glucose results (average, range, standard deviation, number of daily tests) between the study entry, 1 week, 1 month and 3 month follow up visits will be done. Comparison of HbA1c at entry and at 3-month follow-up will be performed. Questionnaire scores will be compared between study entry, 1 week follow up, 1 month follow up and 3-month follow-up visits for DES and Stages of Change scales. We will determine if there is a correlation between the scores on the questionnaires and measures of glucose control. We will classify study and control participants into adherent and non-adherent groups.

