## Study Summary

Title	Use of continuous glucose monitoring system with intensive feedback in adolescents with poorly controlled type 1 diabetes
Short Title	Use of continuous glucose monitoring system with intensive feedback in adolescents with poorly controlled type 1 diabetes
Protocol Number	16-01011
NCT Number	NCT03020069
Principal Investigator	[name]
Methodology	Randomized open label
Study Duration	Estimated duration for the main protocol (e.g. from start of screening to last subject processed and finishing the study)
Study Center(s)	Single-center or multi-center. If multi-center, note number of projected centers to be involved.
Objectives	to determine if using a glucose sensor helps adolescents with t1D understand their range of options in controlling their diabetes
Number of Subjects	60
Diagnosis and Main Inclusion Criteria	Adolescents with type 1 diabetes and an HbA1c $\geq 8\%$

CONFIDENTIAL

This material is the property of the NYU School of Medicine and Langone Medical Center. Do not disclose or use except as authorized in writing by the study sponsor

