
### AIM:

To determine if short-term use of continuous glucose monitoring systems (CGMS) with intensive real time feedback about diabetes management from medical staff to the patient will affect motivation and/or behavior, in adolescents with poorly controlled type 1

CONFIDENTIAL

This material is the property of the NYU School of Medicine and Langone Medical Center. Do not disclose or use except as authorized in writing by the study sponsor

Use of continuous glucose monitoring system with intensive feedback in adolescents with poorly controlled type 1 diabetes  
Version Date: 04/26/2018

diabetes. Previous CGMS studies have tended to focus on participants who are in better glycemic control at baseline and who report better adherence and diabetes-related quality of life than expected of a randomly selected sample of subjects with type 1 diabetes.

Studying a more broadly representative group that includes subjects with poor glycemic control will provide helpful information about glycemic and psychological effects of CGMS in an at risk group(1). Research indicates that various psychological skills and psychosocial factors, including coping and social support play a large role in the efficacy of CGMS use(2).

We hypothesize that short-term CGMS use with feedback (and/or lack thereof) and patients' sense of self-efficacy will influence their stage of change and potentially glucose levels.

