#### CONFIDENTIAL

This material is the property of the NYU School of Medicine and Langone Medical Center. Do not disclose or use except as authorized in writing by the study sponsor

Use of continuous glucose monitoring system with intensive feedback in adolescents with poorly controlled type 1 diabetes  
Version Date: 04/26/2018

Dichotomizing participants into adherent and non-adherent:

Study subjects will receive points for calibrating the CGM device and for successfully completing phone contact with the pediatric diabetes team. The patient will receive 2 points for calibrating the device 2 times/day for at least 5 days, 1 point for calibrating the device 2 times on at least 3 days and 0 points for calibrating any less. Similarly the patient will receive 2 points for completing successful phone contact with study personnel for at least 5 days, 1 point for completing phone contact on at least 3 days and 0 point for contact any less than mentioned before. The two scores will be added to get a total score. Patients with scores 3-4 will be classified as adherent and scores 0-2 will be classified as non-adherent. Control subjects who complete 4 or more phone calls on different days will be classified as adherent and those who complete fewer phone calls will be classified as non-adherent.

Statistical methods:

Demographic data will be tabulated. Statistical analysis of questionnaires will be done according to published standards. The paired t-test will be used for comparisons involving stages of change score.

Independent variables will include the empowerment score, average glucoses, HbA1c and whether the subjects fall into the adherent vs. non-adherent groups. Dependent variables include glucose level(s) and stage of change. We will analyze the 7 day average glucose by meter download and categorize the results in terms of change: No change (-15 to + 15), Higher ( $\geq + 15$ ) or Lower ( $\leq -15$ ). We will analyze the HbA1c and categorize the results in terms of change: No change ( $> -0.5$  to  $+ 0.5$ ), Higher ( $\geq + 0.5$ ) or Lower ( $\leq -0.5$ ). Stages of change (Appendix A) will be categorized as unchanged, improved or worsened. In addition, descriptive statistics including quality of life, diabetes knowledge scale, and demographic variables will be tabulated.

Statistical Analysis for sensor study:

Questionnaires:

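### The plan designates no primary outcome, time point or CGMS-versus-control contrast, and its statements of the main question do not line up

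*Combined protocol and SAP*

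**What the plan says.** Four places in the protocol bear on what the trial is meant to answer.

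- **Study Summary, Objectives:** "to determine if using a glucose sensor helps adolescents with t1D understand their range of options in controlling their diabetes". No instrument or time point is attached.
- **AIM:** the question is whether short-term CGMS use with feedback "will affect motivation and/or behavior, in adolescents with poorly controlled type 1" diabetes. The hypothesis that closes this section is that CGMS use with feedback, and self-efficacy, "will influence their stage of change and potentially glucose levels".
- **ANALYSIS, opening paragraph:** "Measures of the level of glycemic control will be assessed primarily by HbA1c", with average meter glucose ranked second. It then lists the comparisons: "Comparison of the glucose results (average, range, standard deviation, number of daily tests) between the study entry, 1 week, 1 month and 3 month" visits, and "Comparison of HbA1c at entry and at 3-month follow-up will be performed". The DES and Stages of Change scores are also compared across entry, 1 week, 1 month and 3 months.
- **ANALYSIS, Statistical methods:** "Dependent variables include glucose level(s) and stage of change". HbA1c appears in the list of independent variables. The same paragraph nevertheless sorts HbA1c change into higher, lower or unchanged, as one would for an outcome.

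The SUBJECTS section randomises 40 participants to CGMS and 20 to control. The sample size is tied to no outcome. The tests mentioned are a paired t-test for stage of change, rank and t tests between compliant and non-compliant groups, and univariate correlations. No test of CGMS against control is specified for any outcome.

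**The concern.** A reader of the AIM would judge the trial on stage of change. A reader of the opening of ANALYSIS would look to HbA1c. A reader of the Study Summary would look for a measure of understanding, but the nearest instrument, the Diabetes Knowledge Test, is given only at baseline and so cannot show change.

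With no designated primary outcome and no ranking across domains, a favourable result on any scale at any visit could be presented as the trial's answer. The false-positive risk attached to such a claim is then that of the whole set of comparisons, not of a single test. In addition, the listed comparisons run from entry to follow-up. Taken alone, they do not use the control group, which is the reason for randomising.

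**Working it through.** **No figure to reproduce.** The documents give 60 participants (40:20) but no alpha, power, effect size, standard deviation or multiplicity rule. The check is therefore a count of planned comparisons and the error rate that follows. The 0.05 two-sided level per test is my assumption.

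**Step 1: count each follow-up visit against entry.**

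| Outcome | Source | Comparisons |
|---|---|---|
| Meter glucose: average, range, SD, tests per day, at 3 visits | ANALYSIS | 4 × 3 = 12 |
| HbA1c at 3 months | ANALYSIS | 1 |
| DES at 3 visits | ANALYSIS | 3 |
| Stages of Change at 3 visits | ANALYSIS | 3 |
| *Subtotal* | | *19* |
| PHQ-2 at 3 months | METHODS, visit #4; Statistical Analysis for sensor study | 1 |
| *Subtotal* | | *20* |
| PedsQL at 1 and 3 months | METHODS, visits #3 and #4; Statistical Analysis for sensor study | 2 |
| *Total* | | *22* |

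The two PedsQL comparisons are the least certain. The questionnaire is given before and after the intervention, but Statistical methods places quality of life among the descriptive statistics.

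The count omits the categorised versions of glucose, HbA1c and stage of change, the Family Management Measure, the adherence-group comparisons and the questionnaire–glucose correlations. Reading the visit comparisons as all pairs of visits would give 41. I use the smaller count.

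**Step 2: error rate if the tests are independent,** 1 − 0.95^k:

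- k = 19: 1 − 0.95^19 = 0.623
- k = 20: 1 − 0.95^20 = 0.642
- k = 22: 1 − 0.95^22 = 0.676; expected false positives 22 × 0.05 = 1.1

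**Step 3: error rate if the tests are correlated.** These outcomes come from the same participants, so independence gives the high end. Simulation of equally correlated normal statistics (200,000 draws, two-sided 1.96 cut-off) gives:

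| Common correlation | k = 19 | k = 20 | k = 22 |
|---|---|---|---|
| 0.3 | – | – | 0.57 |
| 0.5 | 0.41 | 0.42 | 0.44 |
| 0.7 | – | – | 0.30 |
| 0.8 | – | – | 0.23 |

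The correlations are illustrative; the documents give none.

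**Step 4: compare with one designated test.** A single pre-specified primary comparison carries the chosen level, here 0.05. This is not a like-for-like contrast with the figures above: those concern changes from entry, while the designated test would be between arms. It shows what naming one test does to the error rate on the main question.

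**The case against.** The best defence is that the sections are compatible. An objective, an aim and a within-domain ranking can coexist, and the hypothesis in AIM agrees with the dependent variables in Statistical methods: stage of change, with glucose as a further possibility. Much of this stands, and it rules out several stronger readings.

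- A reader might infer that the sections each name a different primary outcome. They do not. The Study Summary and AIM state objectives without instruments, and the ranking of HbA1c applies only to measures of glycaemic control.
- A reader might infer that HbA1c is already the primary outcome, or that it has been excluded as an outcome. Neither follows. The ranking is silent on the motivational and behavioural domain. The list of dependent variables is not worded as exhaustive, HbA1c change is itself categorised for analysis, and average glucose also appears in both lists.
- A reader might infer that every scale is tested at every visit. It is not: HbA1c and PHQ-2 have one follow-up, PedsQL is not given at 1 week, the knowledge test is baseline only, and CGM satisfaction is collected once in one arm.
- A reader might take the and/or in the AIM to mean that success in either domain suffices. The plan states no success criterion at all.

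The defence does not supply what is missing. Even where the hypothesis and the dependent variables agree, they leave two outcomes, several visits and no between-arm test. Nor can the plan be excused as purely exploratory: it states a hypothesis, randomises, and does not label these comparisons exploratory.

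**Conclusion.** The concern holds as a missing designation combined with statements of purpose that point in different directions. There is no primary outcome, primary time point, CGMS-versus-control contrast or multiplicity rule.

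Across the plausible counts of 19 to 22, the chance of at least one false positive is about 62–68% under independence and about 41–44% at a common correlation of 0.5. For 22 tests it falls to about 30% at 0.7. These figures rest on an assumed alpha of 0.05, on assumed correlations, and on the true absence of any change. The range is wide, but every value in it is well above 5%, and dropping PedsQL or PHQ-2 does not alter the conclusion. The gap limits how any positive result could be interpreted and should be corrected.

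**What to change.** Reconcile the Study Summary, the AIM, the opening of ANALYSIS and the Statistical methods paragraph on one primary outcome at one time point. Analyse it as CGMS versus control, with the entry value of that outcome as covariate, and state the significance level.

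The documents support two candidates:

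- HbA1c at 3 months, following the ranking in ANALYSIS. It is already measured in both groups at entry and at visit #4.
- Stage of change, following the hypothesis in AIM and the dependent variables in Statistical methods. The sponsor would also have to fix the visit, and whether the score or the improved/unchanged/worsened category is analysed.

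The choice is the sponsor's and should be made and recorded before looking at outcome data. Label all other scales and visits secondary or exploratory, and report them with confidence intervals and no success claim.

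The cost is protocol wording, with no new data collection. The real concession is that the sponsor can no longer claim success on a different scale.
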